Specific Aim 1: Determine whether Veterans with MS who receive oral MitoQ in comparison to those who receive placebo have less fatigue after a 12-week treatment period as measured by MFIS Score. Our hypothesis is that MitoQ preserves or improves the mitochondrial function and that in turn may improve fatigue in MS therefore MS veterans taking MitoQ will have less fatigue than those Veterans with MS taking placebo.

Introduction: Fatigue, a common MS symptom can be a cause of significant disability, and loss in quality of life in Veterans with MS. While the mechanisms responsible for fatigue in MS are poorly understood it is possible that reversible mitochondrial dysfunction due to oxidative stress and resultant neuronal ATP depletion may contribute to fatigue. Orally administered MitoQ is a mitochondria-targeted antioxidant similar to CoQ10 but more effective in migration to mitochondria compared to CoQ10 and is aimed at reducing the effects of mitochondria-derived ROS, which lead to mitochondrial dysfunction. While a pilot study using CoQ10 for fatigue improvement in MS showed positive results, studies evaluating effects of oral MitoQ in MS have not been conducted.

Procedures: We will determine the effects of 20 or 40 mg oral MitoQ versus placebo on MS fatigue as measured by MFIS. We will obtain descriptive information about changes in MFIS scores for each subject group and will use the collected data to determine the mean, SD, and confidence interval of this change. This information will also help determine sample size and power analysis for a future phase II trial. This study will be the first to assess whether MitoQ changes fatigue in MS subjects. Data from MFIS scores taken at baseline assessment, and 6- and 12-week time points will be assessed, to determine changes in MFIS fatigue scores. The primary outcome measure will be the change from baseline total MFIS score to 12-week total MFIS score. Secondary outcome measures will be the change from baseline to each of the following measures: 6-week MFIS and 6 and 12-week FSS scores.

Statistical Analysis

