Data Analysis: We will obtain descriptive information on primary and secondary outcomes. In particular, at each time-point, we will obtain the mean, median, SD, and range for each measure and for the changes from baseline for each measure, for the MitoQ and placebo subject groups. We will also obtain 95% confidence intervals for the changes from baseline for each measure, at each time point for both subject groups. We will conduct a t-test to compare primary and secondary measures (changes from baseline) and to obtain the associated 95% confidence intervals for the differences in mean change between the MitoQ and placebo subject groups. We will focus on the confidence intervals that describe the plausible differences in mean change between the subject groups. These confidence intervals will provide information about the magnitude of differences in MFIS and FSS changes between subject groups that are consistent with the previous data. We will also test for differences in the change scores by group in a linear regression framework, adjusting for demographic and clinical characteristics, such as gender. As a secondary analysis, we will use an ANCOVA test with 12-week MFIS score as the outcome and baseline MFIS score as a covariate to account for baseline differences in fatigue among patients. We will use a linear mixed model to analyze MFIS changes over time with fixed effects for time, incorporating baseline values of the outcome as a covariate, and random intercepts and slopes for individuals to incorporate within-subject variability. Due to the exploratory nature of this study, the 6 week time point will provide evidence of whether or not change is seen by 6 weeks. It will allow us to understand how long MitoQ takes to have an effect, and this information will be useful for planning future studies. Both formal hypothesis testing and confidence interval estimation will be conducted. To detect a trend in the effect of MitoQ dosage, we will perform an ANOVA trend analysis on the change in MFIS between baseline and 12 weeks among the three treatment groups. In addition, we will categorize participants who improved by a reliable change, defined as differences in group means divided by the standard error, greater than 1.96 points and test for differences in the proportion of improvers by group using a chi-squared test. The standard error is given by $s_1\sqrt{1 - r_{xx}}$, where s_1 is the standard deviation of the control group and r_{xx} is the MFIS test-retest reliability (here, given by the MFIS Cronbach's alpha value of 0.81.⁶ This analysis will yield additional power (compared to a 2-sample t-test) and will provide useful data for planning a repeated measures analysis in a future larger trial. Secondary outcomes will be analyzed in the same manner. To test if the effect of MitoQ on FSS depended on compliance, compliance (as measured by pill counting) will be treated as a co-variate in the analyses. Patterns of missing data will be examined to determine if patient characteristics are related to missing follow-up data. Statistical significance is defined as $P < 0.05$. SPSS for Windows Version 15.0 (SPSS Inc., Chicago) and SAS (SAS Institute, Cary, NC) will be used for analysis.

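### MFIS change is compared first by an unadjusted t-test; the planned ANCOVA on baseline MFIS, usually more precise, should be primary at almost no cost

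*Combined protocol and SAP*

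**What the plan says.** Under Specific Aim 1, Procedures, the outcome is defined: "The primary outcome measure will be the change from baseline total MFIS score to 12-week total MFIS score". The same paragraph gives a planning purpose: "This information will also help determine sample size and power analysis for a future phase II trial".

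Under Statistical Analysis, Data Analysis, the first between-group comparison is: "We will conduct a t-test to compare primary and secondary measures (changes from baseline". It supplies 95% intervals for the "differences in mean change between the MitoQ and placebo subject groups", and the plan adds: "We will focus on the confidence intervals that describe the plausible differences in mean change between the subject groups".

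The baseline-adjusted model comes later: "As a secondary analysis, we will use an ANCOVA test with 12-week MFIS score as the outcome and baseline MFIS score as a covariate". The dose-response analysis again uses raw change: "we will perform an ANOVA trend analysis on the change in MFIS between baseline and 12 weeks among the three treatment groups".

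Two further models are planned. One is a regression of change scores "in a linear regression framework, adjusting for demographic and clinical characteristics, such as gender"; baseline MFIS is not named among its covariates. The other is a mixed model over time that takes the baseline value as a covariate; its stated fixed effects are for time, and no treatment term is named.

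No sentence calls the t-test the primary analysis. Its lead status follows from four things: it comes first, it is applied to the primary measure, the plan concentrates on its intervals, and the ANCOVA is labelled secondary.

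**The concern.** A t-test on change from baseline is unbiased in a randomised trial, but it subtracts the whole baseline value, which amounts to assuming a regression slope of 1 of week-12 MFIS on baseline MFIS. When the true slope is lower, part of the baseline noise is carried into the comparison. ANCOVA estimates the slope from the data and removes that noise.

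Two things are at stake. First, the intervals that the plan makes its main result may be wider than those from a model it will run on the same patients. Second, in a small pilot the arms can differ at baseline by chance, and the change-score estimate is then pulled in the direction opposite to that imbalance whenever the slope is below 1.

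**Working it through.** **Inputs.** From the documents: the outcome and models above; three arms (20 mg, 40 mg, placebo); significance at P < 0.05, taken as two-sided to match the 95% intervals. No sample size, power, SD or allocation ratio is given, so there is no figure of the plan's own to reproduce. Assumed: three equal arms; total N of 15, 30 or 60; baseline-to-week-12 correlation ρ from 0.5 to 0.8; k = week-12 SD / baseline SD of 0.8, 1 or 1.2. The MFIS value of 0.81 in the Data Analysis text is a Cronbach's alpha, not this correlation, and serves only as an extra illustrative ρ.

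**Step 1: large samples.** Per-subject variance, in units of the baseline variance:

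- change score: 1 + k² − 2ρk
- ANCOVA: k²(1 − ρ²)
- difference: (1 − ρk)², never negative

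With k = 1 the variance ratio, ANCOVA to change, is (1 + ρ)/2. At ρ = 0.5 it is 0.75 (width ratio √0.75 = 0.866); at ρ = 0.7 it is 0.85 (0.922); at ρ = 0.8 it is 0.90 (0.949). With k = 0.8 and ρ = 0.5 it is 0.48/0.84 = 0.571 (0.756). With k = 1.2 and ρ = 0.8 it is 0.5184/0.52 = 0.997 (0.998), practically no gain, because ρk = 0.96.

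**Step 2: small samples.** ANCOVA pays for the estimated slope and the third arm mean (N − 4 residual degrees of freedom against N − 2) and for chance baseline differences. Simulation (20,000 null trials per setting, bivariate normal) gives the mean width of the 95% interval from the three-arm ANCOVA (average of the two doses minus placebo) divided by that from the two-group t-test on change:

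| N | k | ρ = 0.5 | 0.6 | 0.7 | 0.8 |
|---|---|---|---|---|---|
| 60 | 0.8 | 0.763 | 0.784 | 0.799 | 0.807 |
| 60 | 1.0 | 0.874 | 0.903 | 0.931 | 0.958 |
| 60 | 1.2 | 0.941 | 0.969 | 0.992 | 1.008 |
| 30 | 0.8 | 0.774 | 0.794 | 0.809 | 0.817 |
| 30 | 1.0 | 0.885 | 0.914 | 0.943 | 0.970 |
| 30 | 1.2 | 0.954 | 0.981 | 1.005 | 1.020 |
| 15 | 0.8 | 0.801 | 0.826 | 0.842 | 0.850 |
| 15 | 1.0 | 0.921 | 0.952 | 0.979 | 1.010 |
| 15 | 1.2 | 0.992 | 1.019 | 1.044 | 1.062 |

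ANCOVA is narrower on average in 29 of the 36 settings. At the least favourable point, ρk = 1 (ρ = 0.8, k = 1.25), the ratios are 1.010, 1.022 and 1.061 at N = 60, 30 and 15. At ρ = 0.81 and k = 1 they are 0.961, 0.973 and 1.011. Type I error was 0.047 to 0.053 for both methods.

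**Step 3: cross-check.** For a two-group ANCOVA with k = 1, the approximate width ratio is √[((1 + ρ)/2)(1 + 1/(N − 4))] × t(N − 3)/t(N − 2), where t is the 97.5% quantile. At N = 30 this gives 0.884 for ρ = 0.5, 0.941 for 0.7 and 0.971 for 0.81, close to the simulated 0.885, 0.943 and 0.973.

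**Step 4: single trials.** With k = 1, over ρ = 0.5 to 0.8, the ANCOVA interval is the narrower one in 99% to 83% of trials at N = 60, 90% to 61% at N = 30 and 66% to 41% at N = 15.

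**Step 5: baseline imbalance.** For an imbalance d, the change-score estimate differs from the ANCOVA estimate by about (1 − ρk)d, in the direction opposite to d when ρk < 1. One standard error of d is √(1/n₀ + 1/n₁) baseline SD, with n₀ on placebo and n₁ on MitoQ: √(1/20 + 1/40) = 0.27 at N = 60 and √(1/10 + 1/20) = 0.39 at N = 30. With k = 1 the shift is 0.05 to 0.14 SD at N = 60 and 0.08 to 0.19 SD at N = 30. Over k from 0.8 to 1.2 it is 0.01 to 0.16 and 0.02 to 0.23 SD.

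**The case against.** The strongest reply is that the plan already contains the remedy. The ANCOVA is prespecified, the mixed model also carries baseline, and the regression of change scores would give the same group estimate as ANCOVA if baseline MFIS were among its clinical covariates, which the text leaves open. The adjusted interval and the residual SD for phase II planning will exist whatever the label. This stands: the phase II argument adds little, and what changes is which interval is the headline.

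It can also be said that the hierarchy is unclear rather than wrong. The Statistical Analysis text under Specific Aim 2 describes the primary analysis as including a mixed model. That blurs the ranking but does not make the ANCOVA primary, and it is a further reason to name one model.

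Third, this is an exploratory pilot, the t-test matches an outcome defined as change, and every magnitude is assumed. The less favourable side is real: at k = 1.2, over ρ = 0.5 to 0.8, the ANCOVA interval is narrower in only 90% to 29% of single trials at N = 60, 69% to 27% at N = 30 and 47% to 24% at N = 15. The average loss in those settings is still small: at most about 1% at N = 60, 2% at N = 30 and 6% at N = 15. ANCOVA also carries extra variance when baseline means differ, but the simulated widths already include it. These points limit the strength of the recommendation without reversing it.

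**Conclusion.** The concern holds as a matter of efficiency, not validity. The plan leads with the usually less precise of two models it already intends to fit. Under the assumed three equal arms and ρ of 0.5 to 0.8, the average effect of switching runs from a 24% narrower interval (N = 60, k = 0.8, ρ = 0.5) to a 6% wider one (N = 15, k = 1.2, ρ = 0.8). With equal SDs it is a 3% to 13% gain at N of 30 or 60. The gain shrinks as ρk approaches 1, and any loss is a small-sample one. The actual figure cannot be fixed from the documents. The change is worth making because it is nearly free, but the trial would not be unsound without it.

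**What to change.** Name as the primary analysis an ANCOVA of week-12 MFIS on treatment group (three arms), with baseline MFIS as covariate. Define the primary contrast as the average of the two MitoQ doses versus placebo, which corresponds to the plan's two-group comparison, and report the adjusted difference with its 95% interval. Test the dose trend as a linear contrast in the same model. Keep the t-test on change as a sensitivity analysis and keep the descriptive summaries of change. Align the Specific Aim 2 wording on what the primary analysis contains.

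One clarification is needed: Table 2 lists MFIS at both Visit 1 and Visit 2, so state which assessment is baseline and confirm that it precedes the first dose.

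The cost is SAP wording only, since both MFIS values are already collected and the model is already planned. The statistical price is two residual degrees of freedom (N − 4 instead of N − 2), noticeable mainly in a very small sample with ρk near or above 1. If the SAP prefers to save one of them, a two-group ANCOVA for the primary contrast would do so, with the trend tested separately.

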1. Determine whether Veterans with MS who receive oral MitoQ in comparison to those who receive placebo have less fatigue after a 12-week treatment period as measured by MFIS Score.	Primary Outcome: MFIS Secondary Outcome: FSS	Double-Blind, randomized groups assigned to either 20 or 40 mg of MitoQ or an identical placebo. Check MFIS, and FSS and SDMT at time 0, 6 and 12 wks
2. Determine whether Veterans with MS who receive oral MitoQ in comparison to those who receive placebo, have improved cognitive function, quality of life and depression using SDMT, MSIS-29 and the BDI–FS scores respectively.	Secondary Outcome: SA-EDSS and BDI.	Double-Blind, randomized groups assigned to either 20 or 40 mg of MitoQ or an identical placebo. Check SA-EDSS and BDI at time 0 and 12 weeks
3. Determine the safety and tolerability of MitoQ in subjects with MS using side effects and blood tests.	Secondary Outcome: Safety.	Monitoring of patient response and reporting/recording AEs
4. Determine whether plasma MitoQ levels in Veterans with MS treated with MitoQ correlate with clinical outcomes of fatigue, cognitive function, quality of life, depression, blood inflammatory immune markers, and markers of oxidative stress.	Secondary Outcome: Plasma levels of oral MitoQ 1 hr post-drug. Plasma and/or PBMC IFN- γ , TNF- α , IL-2, IL-6 and IL-17, MDA, HAE, TAC, NOC and SOD	Data collection on MitoQ plasma levels and inflammatory and oxidative stress markers at baseline, week 6 and 12.

Subject Visits and Assessment Schedule

Table 2. Study Activities

	Week 0	Week 1	Week 7	Week 13	
	Visit 1	Visit 2	Visit 3	Visit 4	
Visit time	2 hours	2.5 hours	2.5 hours	2.5 hours	
Purpose	screen, consent	begin treatment	in clinic follow up	end treatment	Total blood draw amount
Consent	X				
Vital signs	X	X	X	X	
Medical history, physical neurological exam	X			X	
T25W, 9HPT, SDMT		X	X	X	
BDI, FSS, MFIS, MSIS-29	X	X	X	X	
Blood testing CBC w/ diff (4mls) CMP (6mls)	X		X	X	30 mls
Blood draw for plasma MitoQ level (4mls)		X	X	X	12 mls
Blood draw for Inflammatory immune markers 40 mls		X	X	X	120 mls
Medication reconciliation	X	X	X	X	
Urine testing (female)	X		X	X	
Side effect monitoring			X	X	

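### Two MitoQ doses are randomised, but the plan specifies no 20 mg or 40 mg versus placebo difference in MFIS with a confidence interval, and it does not label the primary analysis

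*Combined protocol and SAP*

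**What the plan says.** All references are to the combined protocol and SAP.

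- **Design.** The Overall Design table, Aim 1 row, describes "randomized groups assigned to either 20 or 40 mg of MitoQ or an identical placebo": three arms. The allocation ratio and sample size are not given. Research Design and Methods says that no research exists to guide the choice of dose.
- **What Aim 1 undertakes.** Specific Aim 1, Procedures, states: "We will determine the effects of 20 or 40 mg oral MitoQ versus placebo on MS fatigue". It also offers "descriptive information about changes in MFIS scores for each subject group", with mean, SD and confidence interval of change, partly to size a later phase II trial. The primary outcome measure is named there: change in total MFIS from baseline to 12 weeks.
- **What the analysis specifies.** The Data Analysis paragraph gives within-group intervals of change "at each time point for both subject groups". The t-test and its 95% interval are for "differences in mean change between the MitoQ and placebo subject groups".
- **Dose.** One analysis separates the doses: "we will perform an ANOVA trend analysis on the change in MFIS between baseline and 12 weeks among the three treatment groups".
- **Order of analyses.** The only Aim 1 analysis with a label is the ANCOVA: "As a secondary analysis, we will use an ANCOVA test with 12-week MFIS score as the outcome". The adjusted regression, mixed model, trend and responder analyses carry no rank. The paragraph adds: "Both formal hypothesis testing and confidence interval estimation will be conducted". The Aim 2 Statistical Analysis paragraph later mentions a primary analysis and a mixed model in one phrase.

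**The concern.** Three arms are randomised, yet the comparison that yields an estimate and an interval is worded for two. An analyst who follows the text could finish Aim 1 with a pooled MitoQ versus placebo difference and a trend P value, and with no estimate of what either dose did. The plan concentrates on confidence intervals and wants its data to help size a phase II trial. The sponsor also says there was no research to guide the dose. Per-dose estimates are therefore among the most useful results this pilot could give.

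The pooled difference cannot supply them. Quite different dose patterns produce the same pooled value, and an effect confined to one dose is diluted.

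A lesser matter is that several Aim 1 analyses are listed, formal testing is promised, and none is labelled primary.

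**Working it through.** **1. Is a per-dose difference specified anywhere?**

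| Aim 1 analysis | Groups as worded | Dose versus placebo difference with interval? |
|---|---|---|
| Within-group intervals of change | both groups | no |
| t-test and 95% interval | MitoQ and placebo | no |
| Adjusted regression | by group, coding not stated | not stated |
| ANCOVA | not stated | not stated |
| Mixed model | fixed effects listed are time and baseline | no |
| Trend analysis | three treatment groups | no |
| Responder chi-squared | by group, coding not stated | not stated |

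The reference in Procedures to each subject group can fairly be read as three arms, but it covers change within an arm and not a difference from placebo.

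**2. What the trend analysis can give.** Linear trend weights are n_i × (dose_i − weighted mean dose).

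- Arms 20/20/20, doses 0, 20, 40: mean dose 20, so the weights are proportional to (−1, 0, +1). This is 40 mg versus placebo, and the 20 mg mean drops out.
- Arms 22/20/18 (placebo, 20 mg, 40 mg): mean dose (20×20 + 18×40)/60 = 18.67, and the weights are proportional to (−1, 0.06, 0.94). The exact statement therefore needs equal placebo and 40 mg arms.
- A quadratic component, (1, −2, 1), does use the 20 mg mean. It compares that mean with the average of the other two arms, which is not 20 mg versus placebo.

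**3. What pooling hides.** Take arbitrary MFIS effects for (20 mg, 40 mg) of (0, −10), (−5, −5) and (−10, 0). With equal MitoQ arms each gives a pooled difference of −5. For (0, −10) the pooled value is −10 × 1/3 = −3.3 if the 20:40 allocation is 2:1, and −10 × 2/3 = −6.7 if it is 1:2. The diluted effect is thus one third to two thirds of the true one, and half with equal arms.

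**4. Precision.** The documents give no figure to reproduce. Assumed: 1:1:1 allocation, n = 20 per arm, baseline to week-12 correlation r = 0.6, in units of the raw-score SD.

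- Error SD on change score: √(2(1 − r)) = √0.8 = 0.894. By ANCOVA: √(1 − r²) = 0.8, ignoring chance baseline imbalance.
- Variance factor, pooled: 1/n + 1/(2n) = 0.075. Per dose: 2/n = 0.1.
- Half-width = t quantile × error SD × √(variance factor). The quantile is 2.002 to 2.003 on 58, 57 or 56 degrees of freedom (two-group t-test, three-arm change score, ANCOVA).

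| 95% half-width, SD | Change score | ANCOVA |
|---|---|---|
| Pooled | 0.490 | 0.439 |
| Each dose versus placebo | 0.566 | 0.507 |
| Pooled, n 15–30, r 0.4–0.8 | 0.28–0.70 | 0.27–0.59 |
| Per dose, n 15–30, r 0.4–0.8 | 0.32–0.81 | 0.31–0.68 |

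Per-dose to pooled ratio: √(0.1/0.075) = √(4/3) = 1.155.

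**5. Power if only one dose works.** Assumed effect 0.8 SD, so the pooled difference is 0.4 SD. Power is from the noncentral t distribution, with noncentrality equal to effect divided by SE.

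| Comparison | Effect / SE | Power |
|---|---|---|
| Pooled, two-group t-test | 0.4 / 0.261 = 1.53 | about 32% |
| Pooled, change score, three-arm error | 0.4 / (0.894 × 0.274) = 1.63 | 36% |
| Pooled, ANCOVA, three-level arm factor | 0.4 / (0.8 × 0.274) = 1.83 | 43% |
| Active dose versus placebo, change score | 0.8 / (0.894 × 0.316) = 2.83 | 79% |
| Active dose versus placebo, ANCOVA | 0.8 / (0.8 × 0.316) = 3.16 | 87% |

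In the first row, the difference between the two MitoQ arms inflates the error variance: 40 × 0.4² / 58 = 0.110, so 0.8 becomes about 0.910 and the SE is √(0.910 × 0.075) = 0.261.

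Over n 15–30 and r 0.4–0.8, power for the active dose is 50–99.8% on change score and 65–99.9% by ANCOVA. At n = 20 over the same correlations, the pooled two-group t-test has 23–52%. The 0.8 SD effect was not varied. If both doses work by 0.8 SD (n = 20, r = 0.6), the pooled t-test has 89%, so pooling does well in that case.

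**The case against.** The strongest reply is that every formal statement of Aim 1 compares MitoQ with placebo, undivided by dose. The Procedures sentence may then describe a single MitoQ group given either dose. On that reading the two-group t-test answers the aim, the trend analysis is the dose analysis, and only a secondary estimate is missing. Much of this stands: the pooled contrast is a legitimate primary comparison, and pooling is inferred from the two-group wording because the text never says it outright. It remains that no per-dose estimate is specified.

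A reader might also infer stronger faults, which the documents do not support:

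- *That dose is ignored.* It is not, because a three-group trend analysis is planned.
- *That the trend analysis says nothing about 20 mg.* This needs a linear-only test with equally spaced scores and equal placebo and 40 mg arms. The text does not say linear.
- *That the primary analysis cannot be known.* The primary outcome is named, the t-test is applied to it, the plan focuses on the resulting intervals, and ANCOVA is called secondary. The t-test is primary by clear implication. The Aim 2 phrase can be read as placing the mixed model in the primary analysis or in the exploratory Aim 2 analyses.
- *That the rise from 32% to 43% is what the ANCOVA covariate buys.* Much of it comes from the three-arm error term. The change-score contrast with that error has 36%, and a two-group ANCOVA also has about 36%.

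**Conclusion.** The point holds as an omission in an exploratory pilot. It should be fixed, but it does not undermine the trial. As written, the plan yields a pooled difference and a trend test, and it specifies no difference with an interval for either dose. That finding rests on the text and needs no assumption.

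Its size does rest on assumptions. Under the stated example, an effect confined to one dose has about a one-in-three chance of detection by the pooled t-test, against about four in five for that dose versus placebo. Dilution to exactly half requires equal MitoQ arms, and the allocation is not stated. The missing primary label is a smaller fault, because the intended analysis can be inferred. Nothing in the documents says that any one of the listed tests reaching P < 0.05 would count as success, so no such charge is made.

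**What to change.** 1. Add the 20 mg versus placebo and 40 mg versus placebo differences in 12-week MFIS change, each with a 95% interval, as secondary estimates. State that mean, SD and interval of change are given for each of the three arms.
2. Label one primary analysis: the pooled MitoQ versus placebo contrast at two-sided 0.05. State how the two doses are weighted (equally or by arm size) if the arms are unequal. The preferred model is the ANCOVA already planned, with 12-week MFIS as outcome, baseline MFIS as covariate and a three-level arm factor. With baseline as covariate, the arm difference is the same for the 12-week score and for change, so the named outcome is kept. Keeping the change-score t-test as primary, with two change-score contrasts added, also closes the gap.
3. Label the remaining Aim 1 analyses supportive, and reword the Aim 2 phrase so that it is clear where the mixed model belongs.

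**Cost.** SAP wording and two contrasts on data already collected. Per-dose intervals are 1.155 times as wide as pooled ones. Making ANCOVA primary reverses the sponsor's order, and the reason is precision (0.44 against 0.49 SD pooled, 0.51 against 0.57 SD per dose, in the example). The pooled contrast stays diluted under either model if only one dose works. If the two per-dose comparisons were read as unadjusted tests, the chance of at least one false positive would be about 9% with a shared placebo arm. That is a reason to present them as estimates.

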
Anticipated results: We expect that MS veterans taking MitoQ for 12 weeks will have less fatigue than those Veterans with MS taking placebo as determined by the MFIS.

Specific Aim 2: Determine whether Veterans with MS who receive oral MitoQ in comparison to those who receive placebo have improved cognitive function, quality of life and depression using Symbol Digit Modality Test (SDMT), MS Impact Scale -29 (MSIS-29) and the Beck Depression Inventory–Fast Screen scores respectively. Our hypothesis is that by improving mitochondrial function in sub optimally functioning neurons and axons, MitoQ, an efficient mitochondrial targeted therapy, may lead to cognition, quality of life and depression improvement in Veterans with MS.

Introduction: In addition to fatigue, cognitive impairment, poor quality of life and depression are some aspects of MS that have significant adverse impact on patient's lives and not addressed by current treatment options including the disease modifying therapies. Mitochondrial targeted therapy CoQ10 has shown significant improvement in depression (BDI) and quality of life in a small pilot study as compared to placebo.⁴⁶ Since MitoQ is considered to have better mitochondrial penetration than CoQ10, it is worthy of exploring its effects on these poorly managed MS symptoms.

Procedures: At baseline assessment and visits 3 and 4 (6 and 12-week post treatment initiation assessment). At each of these visits, we will also acquire data on each subject's cognitive function using SDMT, quality of life assessment using MSIS-29 and depression using BDI-FS scores.

Statistical Analysis: Exploratory analyses similar to the primary analysis including mixed model that will account for repeated measures will be conducted using the SDMT, MSIS-29 and BDI-FS as the secondary outcome measures. To test if the effect of MitoQ depended on changes in depression a similar model will be constructed including both the baseline and the end of the period BDI-FS. The effect of MitoQ on depression will be evaluated by fitting a model with BDI-FS at the end of each period as the outcome. Baseline values for the SDMT, MSIS-

29, BDI-FS and FSS will be included as covariates, and patient effects treated as random. Changes in activity over time will be analyzed in an exploratory manner using graphical techniques.

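### The supporting MFIS mixed model names no treatment or treatment-by-visit term, so as written it cannot show when a MitoQ effect appears, and two follow-up visits poorly support its random slope

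*Combined protocol and SAP*

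**What the plan says.** All references are to the combined protocol and SAP.

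- **Model.** Specific Aim 1, Data Analysis, plans a linear mixed model for MFIS over time "with fixed effects for time, incorporating baseline values of the outcome as a covariate, and random intercepts and slopes for individuals". No treatment or dose term is listed there, and no other section adds one. No covariance structure is given for the random effects.
- **Purpose of week 6.** The same paragraph says of the 6-week time point: "It will allow us to understand how long MitoQ takes to have an effect".
- **Other group comparisons.** That paragraph does name the groups elsewhere: t-tests and adjusted regression on changes from baseline, and a dose-trend ANOVA at 12 weeks.
- **MFIS time points.** Specific Aim 1, Procedures: "Data from MFIS scores taken at baseline assessment, and 6- and 12-week time points will be assessed".
- **Table 2.** The row "BDI, FSS, MFIS, MSIS-29" is marked at all four visits, including screening. The row "T25W, 9HPT, SDMT" is marked at visits 2, 3 and 4 only.
- **Aim 2.** Its Statistical Analysis plans "Exploratory analyses similar to the primary analysis including mixed model that will account for repeated measures" for SDMT, MSIS-29 and BDI-FS, and adds: "To test if the effect of MitoQ depended on changes in depression a similar model will be constructed".

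**The concern.** When a treatment starts to work is a treatment-by-time question. A model with only visit and baseline as fixed effects describes how the whole sample moves, with the three arms mixed together. It contains no MitoQ-minus-placebo contrast at either visit, nor the change in that contrast between visits.

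The planned t-tests give the difference at week 6 and the difference at week 12. They do not give the change between those two differences with a valid standard error, because both tests use the same patients. A mixed model with a treatment-by-visit term would supply it, and would also use patients who miss one follow-up visit.

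The random slope is a second, separate problem. Once baseline is a covariate, each patient contributes only weeks 6 and 12, which is too little to separate an intercept variance, a slope variance, their covariance and a residual variance. The likely results are non-convergence, a boundary estimate, or an unplanned simplification of the model after the data are in.

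**Working it through.** The documents give no sample size, MFIS SD or visit variances, so there is no planned figure to reproduce. The parameter counts in step 3 need only the visit schedule. Every other figure rests on assumed values.

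**1. What the fixed effects can show.** Assume equal arms and these mean MFIS changes at week 6 / week 12:

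| | Placebo | 20 mg | 40 mg | Mean over arms |
|---|---|---|---|---|
| No effect | -2 / -4 | -2 / -4 | -2 / -4 | -2 / -4 |
| Graded effect | 0 / 0 | -2 / -4 | -4 / -8 | (0-2-4)/3 = -2; (0-4-8)/3 = -4 |

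The model as written depends only on the last column and returns a visit change of -2.0 in both cases. With treatment and treatment-by-visit added, the graded case gives differences from placebo of -2.0 (20 mg) and -4.0 (40 mg) at week 6, widening by a further -2.0 and -4.0 at week 12.

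A second simulation (2,000 per arm; baseline SD 15, patient SD 8, residual SD 7) does not rely on matched pooled means. A constant benefit of 10 points in both MitoQ arms left a visit coefficient of +0.02. A benefit of 0 then 10 gave -6.65, which is about two thirds of 10, the MitoQ share of the sample. With the treatment terms (doses pooled), the 0-then-10 case gave -0.05 at week 6 and a further -10.16 by week 12.

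**2. Using the two t-tests instead.** With equal variances and correlation ρ between the week-6 and week-12 changes, the variance of the change in treatment difference is proportional to 2(1-ρ). Treating the tests as independent uses 2. The SE is therefore overstated by 1/√(1-ρ): 1.41 at ρ = 0.5, 1.58 at 0.6 and 2.24 at 0.8.

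**3. Identifying the random effects.** Let the intercept variance be a, the covariance c, the slope variance s and the residual variance r. At weeks 6 and 12:

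- V11 = a + 12c + 36s + r
- V12 = a + 18c + 72s
- V22 = a + 24c + 144s + r

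That is 3 equations in 4 unknowns. Two different parameter sets show the result:

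- (a, c, s, r) = (60, -1, 0.5, 50): V11 = 60-12+18+50 = 116; V12 = 60-18+36 = 78; V22 = 60-24+72+50 = 158.
- (195, -14.5, 2, 23): V11 = 195-174+72+23 = 116; V12 = 195-261+144 = 78; V22 = 195-348+288+23 = 158.

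The slope variances differ fourfold, yet the two sets cannot be told apart from the data. Because V is the same, the GLS fixed effects are the same too.

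With c = 0 there are 3 equations and 3 unknowns, and s = (V22 - V11)/108. The slope variance then rests entirely on week-12 variance minus week-6 variance. Simulating 20,000 covariance matrices per cell (a = 60, r = 50, residual df = N-4) gives the share of trials with an estimate of zero or below:

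| True s | SD ratio, week 12 / week 6 | N = 30 | N = 60 | N = 90 |
|---|---|---|---|---|
| 0 | 1.00 | 0.50 | 0.50 | 0.51 |
| 0.10 | 1.05 | 0.40 | 0.34 | 0.30 |
| 0.25 | 1.11 | 0.26 | 0.17 | 0.12 |

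**4. The screening score.** If the visit 1 MFIS were the covariate and visits 2 to 4 (weeks 0, 6 and 12 of treatment) the responses, there would be 6 covariance elements for 4 parameters, and the model would be identified. The plan does not say this. SDMT has no screening assessment, so that route is not available for it.

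**The case against.** The strongest reply is that the missing term is drafting shorthand. The ANCOVA described just before the mixed model also names no treatment factor, and Aim 2 refers to a similar model when it tests whether the effect of MitoQ depends on depression. A MitoQ term was therefore probably intended. That is likely right, but it leaves open whether treatment has two levels, as in the t-tests, or three, as in the trend test, and whether it interacts with visit.

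The other objections have some force:

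- The week-6 question is partly answered already by the t-test and the adjusted regression on 6-week change. The change in treatment difference between visits is nowhere named as a target, and a t-test on week-12-minus-week-6 scores would give it with a valid SE. That test is not planned, and it would drop patients missing either visit.
- The matched means in step 1 were chosen to make the point, and the plan does not propose combining the t-tests as in step 2.
- The boundary rates fall if variance grows more over time. For V = [[116,78],[78,158]], where the SD ratio is √(158/116) = 1.17, they are 17%, 8% and 4% at N = 30, 60 and 90.
- Aim 2 describes patient effects as random without naming a slope, and one sentence there speaks of evaluating the effect of MitoQ on depression. Carry-over of both defects to Aim 2 is therefore possible but not certain.

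These points limit the weight of the concern. They do not supply the missing terms or the missing covariance structure.

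**Conclusion.** The concern holds. As written, the MFIS mixed model estimates a course pooled over arms and cannot address the onset question the plan sets for the week-6 visit. That conclusion rests on the text and needs no assumed values.

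The random slope is not identified with two responses per patient if it is correlated with the intercept, and only just identified if it is independent. This assumes that baseline is a covariate and not also a response, as the model sentence reads. It affects convergence and variance components, not whether a treatment contrast can be estimated. How often the slope variance would reach zero depends on unknown visit variances: from about 50% down to 4% over the values shown.

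The primary 12-week comparison is unaffected. This is a moderate defect in a supporting, exploratory analysis and should be fixed.

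**What to change.** Replace the mixed-model sentence with a full specification:

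- **Response:** MFIS at weeks 6 and 12.
- **Fixed effects:** treatment (placebo, 20 mg, 40 mg), categorical visit, treatment-by-visit and baseline MFIS.
- **Covariance:** unstructured within patient, or a random intercept only; no random slope.
- **Reported results:** each dose minus placebo with a 95% CI at weeks 6 and 12, and the week-12-minus-week-6 change in each contrast. If a result to set beside the two-group t-test is wanted, name a pooled MitoQ contrast as well.
- **Baseline:** state whether it is the visit 1 or the visit 2 score. This is a minor clarification that comes with the rest.

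Use the same form for SDMT, MSIS-29 and BDI-FS in Aim 2. The cost is SAP wording and a few lines of code, with no new data or visits.
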